9.3 Populations for Analyses

All participants enrolled and dosed will be included in the safety population and the safety analyses. All participants who had at least one interpretable PK sample will be included in the PK analysis.

9.4 Statistical Analyses

9.4.1 General Approach

Analyses will be presented by treatment cohorts. There are 2 planned treatment cohorts: 1) participants receiving caffeine dosing in Cohort 1; and 2) participants receiving caffeine dosing in Cohort 2.

Descriptive statistics

Descriptive statistics such as number of observations, mean, median, standard deviation, standard error, minimum and maximum will be presented by treatment groups for continuous variables (such as age, weight, etc.). Other descriptive statistics such as counts, proportions, and/or percentages will be presented by group to summarize discrete variables (such as race, sex, etc.).

PK analysis plan

PK parameters will be estimated by population PK approach using nonlinear mixed effects modeling in NONMEM (Icon Development Solutions, [name]). The influence of covariates on PK parameters, such as gestational age, postnatal age, serum creatinine and transaminases, oliguria, and concomitant medications will be explored.

Safety

The number and percent of AEs and SAEs within each cohort will be summarized overall as well as by each Medical Dictionary for Regulatory Activities (MedDRA) system organ class and preferred term. Laboratory data will be tabulated by dose groups. Summary statistics for changes from baseline will be presented.

9.4.2 Analysis of the Primary Endpoint(s)

- **Pharmacokinetics**

We will perform a population PK analysis using nonlinear mixed effects methodology implemented in the software NONMEM (Icon Development Solutions, [name]) to analyze caffeine concentration data. We will compare clearance to expected values based on gestational age and birth weight.^{59,60} Since the PK of caffeine is well-described in the literature, we will focus our analysis on the effects of HIE and therapeutic hypothermia on caffeine PK. Significant covariates (e.g., gestational age, postnatal age, serum creatinine and transaminases, oliguria, concomitant medications) will be evaluated using forward addition ($P<0.05$) with backward elimination ($P<0.01$) approach.

9.4.3 Analysis of the Secondary Endpoint(s)

- **Preliminary Effectiveness**

We will use MRI brain images from enrolled neonates to assess the severity of brain injury according to the scoring strategy used in the NICHD trial: 0 (normal MRI), 1A (minimal cerebral lesions), 1B (extensive cerebral lesions), 2A (basal ganglia thalamic injury), 2B (2A with cerebral lesions), and 3 (hemispheric devastation). We will dichotomize these results into normal and abnormal and use logistic regression to compare neonates in cohorts 1 and 2 to treated neonates in the NICHD trial to calculate a risk ratio for abnormal MRI with 95% confidence

intervals, adjusting for potential confounders such as severity of encephalopathy and presence of seizures.

We will use the composite cognitive, language, and motor scores on the Bayley-III at the 18-24 month follow-up visit to assess NDI. We will define NDI as any of the following: composite cognitive, language, or motor score < 85, hearing impairment requiring hearing aids, a diagnosis of blindness, or GMFCS level ≥ 3 . We will use logistic regression to compare neonates in cohorts 1 and 2 to treated neonates in the NICHD trial to calculate a risk ratio for NDI with 95% confidence intervals.

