1 PROTOCOL SUMMARY

1.1 Synopsis

Title:	Pharmacokinetics and Safety of Caffeine in Neonates with Hypoxic-Ischemic Encephalopathy
Study Description:	This is a phase I, open-label, dose-escalating pharmacokinetics (PK) and safety study of caffeine in neonates with hypoxic-ischemic encephalopathy undergoing therapeutic hypothermia. We hypothesize that drug clearance will be $\geq 20\%$ lower than expected for gestational age and birth weight and that the incidence of adverse events will be within 20% of published results of neonates treated with therapeutic hypothermia in the NICHD Total Body Hypothermia for Neonatal Encephalopathy trial.
Objectives:	
Primary Objective: Characterize the PK of caffeine in neonates undergoing therapeutic hypothermia for hypoxic-ischemic encephalopathy (HIE).
 
Secondary Objectives: Characterize the safety of caffeine in neonates undergoing therapeutic hypothermia for HIE. Evaluate the preliminary effectiveness of caffeine in reducing brain injury in neonates with HIE.

Endpoints:	
Primary Endpoint: PK: Caffeine clearance
 
Secondary Endpoints: Safety: Adverse events Note: Seizures and necrotizing enterocolitis will be AEs of special interest Preliminary effectiveness: Death, abnormal MRI findings, neurodevelopment at 18-24 months

Study Population:	
Inclusion Criteria
 
 1. Documented informed consent from parent or guardian 2. ≥ 36 weeks gestational age at birth 3. Receiving therapeutic hypothermia for a diagnosis of HIE 4. Intravenous (IV) access 5. Postnatal age < 24 hours 
Exclusion Criteria
 
 1. Receiving > 1 anti-epileptic drug for seizures 2. Sustained (>4 hours) heart rate > 180 beats per minute 3. Known major congenital anomaly 4. Any condition which would make the participant, in the opinion of the investigator, unsuitable for the study
Phase:	1
Description of Sites/Facilities Enrolling Participants:	Up to 3 US Neonatal Intensive Care Units, including The University of North Carolina at Chapel Hill Newborn Critical Care Center

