2 INTRODUCTION

2.1 Study Rationale

Hypoxic-ischemic encephalopathy (HIE) due to perinatal asphyxia is a common and often fatal disease in neonates. HIE occurs in nearly 1% of live births.¹ Neonates with HIE experience a temporary interruption in blood flow to the brain and body around the time of delivery. This results in tissue hypoxia with subsequent damage to the brain and other vital organs.² Encephalopathy manifests as abnormalities in the neurological exam, which can include seizures and alterations in levels of consciousness, muscle tone, and breathing patterns. The severity of encephalopathy is categorized into three stages (mild, moderate, and severe) based on the Sarnat grading scale.³

Therapeutic hypothermia reduces morbidity and mortality in neonates with HIE. Therapeutic hypothermia reduces the risk of death or neurodevelopmental impairment (NDI) at 18-24 months in neonates with moderate to severe HIE (number needed to treat is 7).⁴⁻¹⁰ Even with therapeutic hypothermia, mortality or NDI remains ~60% in neonates with HIE.¹⁰ As a result, there is an **urgent, unmet public health need** to develop adjuvant therapies to improve neurodevelopmental outcomes in this population.

Adjuvant therapies are being investigated to improve outcomes in neonates with HIE (Table 1). These agents primarily target the effects of reperfusion injury in the brain which occurs 6-48 hours following the initial insult as a result of inflammation, oxidative stress, and excitotoxicity leading to cell death.¹¹ All studies, with the exception of erythropoietin and allopurinol, are early phase trials and none of these therapies are currently approved or have demonstrated definitive benefits for HIE. Caffeine has not yet been investigated for neuroprotection in neonates with HIE.

Table 1. Adjuvant therapies under investigation for HIE

Therapy	Clinicaltrials.gov
Erythropoietin ^{12,13}	NCT01913340; NCT02811263*
Darbepoetin alfa ^{14,15}	NCT01471015
Autologous cord blood stem cells ^{16,17}	NCT02612155; NCT02434965
Melatonin ¹⁸	NCT02621944
Xenon ^{19,20}	NCT00934700; NCT01545271
Allopurinol ^{21,22}	NCT03162653**
Topiramate ²³	NCT01241019; NCT01765218
Clonidine	NCT01862250

Anticipated Phase III completion: *September 2022; **December 2020

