5 STUDY POPULATION

5.1 Inclusion Criteria

1. Documented informed consent from parent or guardian
2. \geq 36 weeks gestational age at birth
3. Receiving therapeutic hypothermia for a diagnosis of HIE
4. Intravenous (IV) access
5. Postnatal age $<$ 24 hours

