5.5 Strategies for Recruitment and Retention

We anticipate that 18 neonates will be recruited from up to 3 US NICUs, including the University of North Carolina at Chapel Hill (UNC) Newborn Critical Care Center (NCCC). Enrollment will begin at UNC and expand to other sites, if needed. The decision to provide therapeutic hypothermia will be at the discretion of the clinician. A neonate will be eligible for screening and enrollment in this study as soon as the decision is made by the clinician to provide therapeutic hypothermia for HIE. The parents of neonates undergoing therapeutic hypothermia will be approached for enrollment by study coordinators in a timely fashion to ensure that the first dose of study drug is given prior to 24 hours postnatal age. For neonates enrolled in the study, retention of subjects will be enhanced by close follow-up in the Special Infant Care Clinic, which is the standard of care for all neonates undergoing therapeutic hypothermia for HIE at UNC, or equivalent follow-up clinic at other sites.

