8 STUDY ASSESSMENTS AND PROCEDURES

8.1 Study Procedures

8.1.1 Screening/Baseline

Research staff will screen for eligibility requirements. After the parent or guardian has provided informed consent and after it has been determined that the participant satisfies all inclusion and no exclusion criteria, the following evaluations will be recorded in the CRF:

1. Participant demographics
 - a. Maternal race/ethnicity
 - b. Maternal age
 - c. Inborn/outborn
 - d. Infant sex
 - e. Gestational age (weeks)
 - f. Postnatal age (hours)
2. Neurological exam
 - a. Level of consciousness
 - i. Hyperalert or irritable
 - ii. Lethargic or poorly responsive
 - iii. Minimal or no responsiveness
 - b. Spontaneous activity
 - i. Slightly decreased
 - ii. Decreased
 - iii. Absent
 - c. Posture
 - i. Mild distal flexion
 - ii. Distal flexion, complete extension
 - iii. Decerebrate
 - d. Tone
 - i. Hypertonic
 - ii. Hypotonic
 - iii. Flaccid
 - e. Primitive Reflexes
 - i. Suck
 1. Normal
 2. Weak or bite
 3. Absent
 4. Unable to assess
 - ii. Moro
 1. Low threshold to elicit
 2. Weak or incomplete
 3. Absent
 4. Unable to assess
 - f. Autonomic

- i. Pupils
 - 1. Equal and reactive
 - 2. Constricted
 - 3. Dilated and either fixed or sluggishly reactive; asymmetric
 - 4. Unable to assess
- ii. Respiration
 - 1. Normal
 - 2. Periodic breathing
 - 3. Intubated or ventilated
- 3. Birth weight (grams)
- 4. Medical history
 - a. All Apgar scores (0-10)
 - b. Chest compressions in the delivery room (yes/no)
 - c. Lowest pH among cord arterial, cord venous, and arterial blood gas taken before 1 hour of age
 - d. Sentinel event, defined as placental abruption, shoulder dystocia, uterine rupture, or prolapsed cord
 - e. Severity of encephalopathy based on Sarnat staging³ (mild, moderate, or severe)
 - f. Start time of therapeutic hypothermia
- 5. Respiratory support at time of enrollment (room air, oxyhood, nasal cannula/CPAP, or mechanical ventilation) and maximum FIO₂ exposure during each 24-hour period
- 6. Concomitant medications (see Section 6.5)
- 7. Laboratory evaluations (see Section 8.2.1)

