9 STATISTICAL CONSIDERATIONS

9.1 Statistical Hypotheses

- **Pharmacokinetics**

We hypothesize that drug clearance will be $\geq 20\%$ lower than expected for gestational age and birth weight as a result of HIE and therapeutic hypothermia.

- **Safety**

We hypothesize that frequency of seizures in both treatment cohorts will be within 20% of published results of neonates treated with therapeutic hypothermia in the NICHD Total Body Hypothermia for Neonatal Encephalopathy trial.⁵

- **Preliminary effectiveness**

We hypothesize that the risk ratio for an abnormal MRI prior to discharge will be favorable, i.e., between 0.7 and 1.1 in treated neonates compared to published results of neonates treated with therapeutic hypothermia in the NICHD Total Body Hypothermia for Neonatal Encephalopathy trial.⁵

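### The NDI comparison with NICHD is planned without adjustment for encephalopathy severity, although the MRI comparison with the same group is adjusted, so case mix alone can shift the NDI risk ratio

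*Combined protocol and SAP*

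**What the plan says.** Section 9.4.3 plans two logistic-regression comparisons of cohorts 1 and 2 with treated neonates from the NICHD trial. The one for abnormal MRI is specified as "adjusting for potential confounders such as severity of encephalopathy and presence of seizures". The one for NDI, in the next paragraph, is specified only as "to calculate a risk ratio for NDI with 95% confidence intervals". No covariate is named, and neither Section 9.4.1 nor the rest of Section 9 extends the MRI adjustment to NDI.

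Other sections bear on the comparison:

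- Section 8.1.1 records "Severity of encephalopathy based on Sarnat staging" at baseline, as mild, moderate or severe.
- Section 5.1 admits any infant "Receiving therapeutic hypothermia for a diagnosis of HIE", with no minimum grade. Section 5.5 adds: "The decision to provide therapeutic hypothermia will be at the discretion of the clinician".
- The exclusion criteria remove infants who meet "Receiving > 1 anti-epileptic drug for seizures" at entry.
- Section 2.1 reports the benefit of cooling, citing references 4 to 10 (the NICHD trial is reference 5), "in neonates with moderate to severe HIE (number needed to treat is 7").
- Section 9.1 states the MRI hypothesis as "compared to published results of neonates treated with therapeutic hypothermia in the NICHD Total Body Hypothermia for Neonatal Encephalopathy trial". It gives no NDI hypothesis.

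**The concern.** The comparator is the same non-randomised historical group for both outcomes. The plan itself treats severity as a confounder for MRI and gives no reason to drop it for NDI. Section 2.2 reports that MRI findings were independently associated with NDI, so a confounder of one is a plausible confounder of the other.

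Mild infants can enter this trial and may have no counterpart in NICHD. A crude risk ratio then mixes who was enrolled with what caffeine did. Section 4.2 says the study is a first step towards designing a larger trial, so a shifted NDI ratio could feed into that planning.

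**Working it through.** The plan gives no expected NDI rate, margin or power, so there is no figure to reproduce. The check asks what crude ratio arises when caffeine does nothing.

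**Assumptions (none from the documents).** NDI risk is 10–25% in mild, 30–40% in moderate and 50–65% in severe HIE. NICHD has a severe share s of 25–35%, the rest moderate and none mild. The trial has a mild share m, and its other infants split as in NICHD.

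**Formulas.**

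- NICHD risk: p_H = (1 − s) × r_mod + s × r_sev
- Trial risk: p_T = m × r_mild + (1 − m) × p_H
- Crude RR = p_T / p_H

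**Set A (steeper gradient):** risks 0.10, 0.35, 0.60 and s = 0.35. p_H = 0.65 × 0.35 + 0.35 × 0.60 = 0.4375.

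**Set B (shallower gradient):** risks 0.25, 0.35, 0.50 and s = 0.25. p_H = 0.75 × 0.35 + 0.25 × 0.50 = 0.3875.

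| Mild share m | A: p_T | A: RR | B: p_T | B: RR |
|---|---|---|---|---|
| 10% | 0.404 | 0.92 | 0.374 | 0.96 |
| 20% | 0.370 | 0.85 | 0.360 | 0.93 |
| 30% | 0.336 | 0.77 | 0.346 | 0.89 |
| 50% | 0.269 | 0.61 | 0.319 | 0.82 |

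**Fewer severe infants, none mild.** Take NICHD as one-third severe, the trial as 15% severe, moderate risk 0.20–0.30 and severe risk 0.60–0.70.

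- Lower risks: p_H = 0.333, p_T = 0.85 × 0.20 + 0.15 × 0.60 = 0.26, RR = 0.78.
- Higher risks: p_H = 0.433, p_T = 0.85 × 0.30 + 0.15 × 0.70 = 0.36, RR = 0.83.

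**More severe infants, none mild.** Take the trial as 50% severe.

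- Risks 0.35 and 0.50, s = 0.35: p_H = 0.4025, p_T = 0.425, RR = 1.06.
- Risks 0.30 and 0.60, s = 0.25: p_H = 0.375, p_T = 0.45, RR = 1.20.

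**What adjustment does.** Within each grade the null ratio is 1.00 by construction, so stratifying or standardising removes the shift for grades seen in both groups. It cannot do so for mild infants if NICHD has none. Those infants have to be left out of the comparison.

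**Precision.** For a true RR of 1, the 95% limits are exp(±1.96 × SE), with SE = √[(1 − p)/(n p) + (1 − p)/(h p)]. Assume n = 15–18 infants, h = 70–100 historical controls and p = 0.30–0.40. The widest case (n = 15, h = 70, p = 0.30) has SE = 0.435 and limits 0.43 to 2.34. The narrowest (n = 18, h = 100, p = 0.40) has SE = 0.314 and limits 0.54 to 1.85.

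**The case against.** **The endpoint is preliminary.** Section 8.1.6 says the trial is not powered for efficacy against the historical group, and no NDI threshold or decision rule depends on the ratio. A null ratio of 0.8 lies well inside the intervals above. This stands and limits the consequence. It does not remove the bias, which better precision would not cure, and the plan still commits to a comparative estimate.

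**The magnitude is assumed.** This also stands. The documents give neither stratum risks nor NICHD's severity mix, and with 10% mild infants the shift is small.

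**Severity is not the only problem.** The documents do not show that NICHD used this NDI definition, or how deaths enter the NDI comparison. Severity adjustment repairs neither.

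A reader might infer more than the documents support:

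- *That the adjusted analysis is impossible with published results.* A regression on a categorical covariate can run on grouped counts, which a publication may supply; adding seizures would need counts cross-classified by both factors. The published-results wording in Section 9.1 is also not attached to NDI.
- *That age at entry and the anti-epileptic drug exclusion are known to differ from NICHD.* The documents do not give NICHD's entry window or seizure criteria. Only the missing minimum grade, set against Section 2.1, supports a possible difference.

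**Conclusion.** The point holds as an inconsistency with a practical consequence. One of two comparisons with the same historical group omits a covariate that the plan names as a confounder and already collects. Under the assumed risks and no drug effect, the crude NDI ratio is about 0.61–0.96 with 10–50% mild infants. It is 0.78–0.83 with fewer severe infants and none mild, and 1.06–1.20 with severe infants over-represented. For scale, Section 9.1 calls an MRI ratio of 0.7 to 1.1 favourable.

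It would be tempting to conclude that the plan will manufacture a benefit. The documents do not support that: the actual case mix is unknown and the bias can run either way. The open entry criteria make the favourable direction the more likely one, but no more than that. The harm is a misleading preliminary estimate, not a wrong confirmatory conclusion.

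**What to change.** In Section 9.4.3, before the 18–24 month outcomes are known:

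1. Adjust or standardise the NDI comparison for baseline Sarnat stage. With at most 18 infants, one or two covariates are all that can be supported.
2. Use baseline covariates only. Seizures arising after dosing may be a drug effect and should not be adjusted for. Infants on more than one anti-epileptic drug at entry are excluded, so a seizure as defined in Section 9.4.4.1 would first appear after enrolment.
3. Restrict the comparison to grades present in both groups. If NICHD has no mild infants, report this trial's mild infants descriptively.
4. Name the NICHD data source: individual records, or published NDI counts by severity. Published counts allow a grouped regression, or an observed/expected ratio with an exact confidence interval.
5. State how the risk ratio is obtained, since logistic regression gives an odds ratio (for example standardisation, a log link or modified Poisson regression).
6. If no NICHD NDI data by severity can be obtained, report NDI descriptively by Sarnat grade and drop the comparative ratio.

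On the trial side the cost is wording, because Sarnat stage is already in the CRF. The real cost is obtaining comparator NDI data by severity, possibly through a data request. Leaving mild infants out of the comparison would also reduce an already small sample.

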9.4.4 Safety Analyses

We will collect information on adverse events (AEs) during and after study drug administration. Seizures will be AE of special interest and defined by the receipt of > 1 AED. We will summarize AEs by organ system and report descriptive statistics of laboratory values. We will correlate caffeine exposure with seizure activity and NEC following the first dose of caffeine.

Following the follow-up period in the final cohort 1 participant, there will be an interim safety analysis performed by an independent safety monitor (ISM) with training in neonatology and experience in conducting clinical trials who is not otherwise associated with the study. We will halt enrollment during this analysis. If there is > 1 serious adverse events (SAEs) related to the drug in any cohort, the study will be temporarily halted for an *ad hoc* safety review.

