2.3.3 Assessment of Potential Risks and Benefits

Given the high incidence of mortality and NDI in neonates with HIE, we propose that the value of the information to be gained in this study outweigh the potential risks of exposure to caffeine. We have minimized these potential risks by using a dose of caffeine that is equivalent to the dose ranges used on-label for apnea of prematurity in preterm neonates. We will exclude neonates with difficult to control seizures (i.e., receiving > 1 anti-epileptic drug [AED]), tachycardia (defined as heart rate > 180 beats per minute for > 4 hour), or major congenital anomalies, including congenital heart disease. We will collect data on seizures and necrotizing enterocolitis as safety events of interest. We will review safety data prior to dose escalation between cohorts.

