8.3.8 Events of Special Interest

1. Seizures will be defined by the receipt of > 1 AED, as we are interested in identifying seizures which are difficult to control.
2. Necrotizing Enterocolitis - Bell Stage II or III⁵⁷

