9.2 Sample Size Determination

- **Pharmacokinetics**

A sample size of 9 neonates in each dosing cohort will be powered ($\geq 80\%$) to target a 95% confidence interval within 60% and 140% of the geometric mean estimate of clearance (assuming 36% between subject variability in clearance, which is based on existing literature of caffeine PK in neonates).⁵⁸⁻⁶⁰

- **Safety**

The frequency of seizures in the treated group of the NICHD trial was $\sim 40\%$.⁵ Estimation of the probability of seizures in our study will be based on the combined sample of 18 patients. For comparison with historical data, the null hypothesis that the frequency of seizures is 40% will be rejected if 11 or more adverse events (in 18 patients) are observed. The event probability will be no wider than 21% on each side of the point estimate and this will provide a power of 86%. The alternative hypothesis is that the frequency of seizures is $> 61\%$ or $< 19\%$ in our study (i.e., $> 21\%$ on either side of the point estimate of 40%).

- **Preliminary effectiveness**

This is an exploratory aim and will not be sufficiently powered to detect a significant reduction in brain injury on MRI. However, we estimate that there will be a trend toward risk reduction of brain injury in enrolled neonates compared to treated neonates in the NICHD trial.

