10.1.6 Safety Oversight

Safety oversight will be under the direction of an ISM with expertise in neonatology and clinical trials. The monitor will be independent from the study conduct and free of conflict of interest. The monitor will perform a safety analysis following the treatment period in the final cohort 1 participant and prior to enrollment in cohort 2, or on an *ad hoc* basis if there is > 1 SAE related to the drug in any cohort.

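### The one numeric trigger for unscheduled independent safety review counts drug-related SAEs per cohort and names neither event of special interest, so whether seizures or NEC reach the monitor during cohort 2 depends on site classification

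*Combined protocol and SAP*

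**What the plan says.** Section 9.4.4 halts the study for an ad hoc review "If there is > 1 serious adverse events (SAEs) related to the drug in any cohort". Section 10.1.6 repeats the rule ("if there is > 1 SAE related to the drug in any cohort") and names the ISM as the reviewer. The count must therefore reach two, and on a literal reading it restarts with cohort 2.

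The only scheduled ISM review falls between the cohorts. Section 9.4.4 places it after follow-up ("Following the follow-up period in the final cohort 1 participant, there will be an interim safety analysis"), while Section 10.1.6 has "The monitor will perform a safety analysis following the treatment period in the final cohort 1 participant and prior to enrollment in cohort 2". No ISM review is scheduled after cohort 2 starts, and Section 9.4.6 lists no planned interim analyses. Table 3 (Section 6.1.2) gives the same loading dose in both cohorts and a maintenance dose of 5 mg/kg in cohort 1 and 10 mg/kg in cohort 2.

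Seizures and NEC are the two events of special interest. Section 8.3.8 states: "Seizures will be defined by the receipt of > 1 AED, as we are interested in identifying seizures which are difficult to control"; NEC means Bell stage II or III. Section 2.3.3 offers their collection as part of risk minimisation: "We will collect data on seizures and necrotizing enterocolitis as safety events of interest". Section 9.4.4 will correlate both with caffeine exposure. No count of either prompts a review.

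The only numeric seizure rule is in Section 9.2: reject a 40% frequency if 11 or more of 18 infants have the event. It is a pooled comparison with historical data: "Estimation of the probability of seizures in our study will be based on the combined sample of 18 patients". It is not a monitoring rule.

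**The concern.** The protocol singles out seizures because high caffeine doses may lower the seizure threshold (Sections 2.2 and 3), and it expects clearance to be reduced in these infants (Section 9.1). One would expect the safety rule to respond directly to seizures, particularly at the higher maintenance dose. Instead it responds only to events that pass two site judgements, seriousness and relatedness, in an open-label study without a concurrent control group.

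The relatedness judgement is not well determined for seizures. Under Section 8.3.3.2 a temporal relationship is enough for Related, while an established alternate etiology is enough for Not Related. Section 2.1 describes seizures as a possible manifestation of the encephalopathy itself, so HIE is a candidate alternate cause in every infant. Two sites could class the same post-dose seizure differently, and each could point to the text.

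At stake is whether a cluster of second-AED seizures or NEC cases in cohort 2 would come before the independent monitor while infants are still being enrolled. The same wording means that two related SAEs split between the cohorts, or a single drug-related death, do not by themselves reach the numeric trigger.

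**Working it through.** **The plan's own figures.** The documents give no operating characteristic for the ad hoc trigger, so there is none to reproduce. The nearest stated figure is the 86% power of the 11-of-18 seizure rule. By exact binomial, P(X ≥ 11 | 18, 0.40) = 0.058 and P(X ≥ 11 | 18, 0.61) = 0.598, so 86% does not reproduce at the stated 61% alternative. That is a separate matter, and nothing below depends on it.

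**Inputs.** Cohort size is 9 (Section 4.1). The reference seizure rate is 40% and the upper boundary 61% (Section 9.2). A 20% rate is added as an assumption, because the documents do not say that the 40% uses the more-than-one-AED definition. Let q be the share of seizure events that the site judges both serious and related. The documents give no value for q, so it is varied from 0 to 1.

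**Chance that seizures fire the trigger in cohort 2.** With one event at most per infant, infants independent, and no other SAEs counted, the per-infant probability of a counted event is r = p × q, and

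P(trigger) = 1 − (1 − r)^9 − 9r(1 − r)^8.

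For p = 0.40 and q = 0.25, r = 0.10: 1 − 0.3874 − 0.3874 = 0.225.
For p = 0.40 and q = 0.50, r = 0.20: 1 − 0.1342 − 0.3020 = 0.564.
For p = 0.40 and q = 1, r = 0.40: 1 − 0.0101 − 0.0605 = 0.929.

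| Seizure rate p | Expected in 9 | q = 0 | q = 0.10 | q = 0.25 | q = 0.50 | q = 1 |
|---|---|---|---|---|---|---|
| 20% (assumed) | 1.8 | 0 | 0.013 | 0.071 | 0.225 | 0.564 |
| 40% | 3.6 | 0 | 0.048 | 0.225 | 0.564 | 0.929 |
| 61% | 5.5 | 0 | 0.101 | 0.409 | 0.813 | 0.997 |

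Moving q from 0.25 to 1 at a fixed 40% rate takes the probability from 0.225 to 0.929. Moving the seizure rate from 40% to 61% at q = 0.25 takes it only from 0.225 to 0.409. The classification matters at least as much as the event rate.

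The documents give no NEC rate, so none is computed.

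**Per-cohort against pooled counting.** Let s be the chance that an infant has a related SAE (assumed 5% or 10%; not in the documents).

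- Either cohort reaches two: 1 − [(1 − s)^9 + 9s(1 − s)^8]².
- Pooled over 18: 1 − (1 − s)^18 − 18s(1 − s)^17.
- The difference is the pattern of exactly one in each cohort: [9s(1 − s)^8]².

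At s = 0.10: 1 − 0.7748² = 0.400; pooled 1 − 0.1501 − 0.3002 = 0.550; difference 0.3874² = 0.150.
At s = 0.05: 1 − 0.9288² = 0.137; pooled 0.226; difference 0.089.

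**The case against.** A reader might infer that the two events of special interest are excluded from the trigger, and that any number of them in cohort 2 must pass unreviewed. The documents do not support that. An event that is serious under Section 8.3.2, which includes important medical events, and related under Section 8.3.3.2 counts like any other. The causality text leans towards inclusion: an event known to occur with the drug, or merely linked in time, is Related; the study product is always to be suspected; and the alternate etiology must be established, not just plausible. Section 2.3.1 lists both seizures and NEC among caffeine's risks. The zero column applies only if sites class no seizure as both serious and related. For NEC in particular, nothing shows that it would be classed as unrelated; the point is only that it is not named.

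Other routes exist. SAEs go at once to the investigator, and certain suspected reactions go to FDA within 7 or 15 days (Section 8.3.6). Unanticipated problems that are SAEs go to the IRB within 7 days (Section 8.4.2). The study can be suspended for unacceptable risk (Section 10.1.2), and a second AED is an example ground for withdrawing an infant (Section 7.2). So this is the only numeric trigger, not the only safeguard. None of these routes, however, is tied to a count of special-interest events or guarantees that the ISM is told. Section 10.1.5, on roles and governance, was not available to read, so a further ISM duty there cannot be ruled out.

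It might also be inferred that cohort 2 is monitored less closely by design. During dosing both cohorts have the same ad hoc rule. The scheduled review gates escalation, and a matching review after cohort 2 would gate no further dosing. Nor does the one-per-cohort pattern hide two events: the cohort 1 SAE precedes the scheduled review if it falls within the period which that review covers, so normally only the cohort 2 event would go without ISM review.

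These objections remove the absolute claims. The dependence on site judgement and the ambiguous count remain.

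**Conclusion.** The point holds in this limited form. No count of seizure or NEC events prompts independent review; such events count only through site calls on seriousness and relatedness; and the causality definitions overlap for seizures in HIE. At a 40% seizure rate, the chance that seizures fire the trigger in cohort 2 runs from 0 to 0.93 depending on those calls alone. If the rate on the more-than-one-AED definition is nearer 20%, the range is 0 to 0.56.

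The per-cohort wording lowers the chance of a triggered review from 0.55 to 0.40 at an assumed 10% related-SAE rate, and from 0.23 to 0.14 at 5%. This rests on the literal reading of the phrase about any cohort, which could also be meant cumulatively.

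The results assume independent infants, at most one counted event each, and values of q and s that the documents do not supply. They show how undefined the safeguard is; they do not predict how sites will behave. This is a worthwhile and inexpensive improvement to safety monitoring. It does not show that the trial is unmonitored for seizures.

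**What to change.** Amend Sections 9.4.4 and 10.1.6 together so that:

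- related SAEs are counted cumulatively over both cohorts and all sites;
- every event of special interest and every death is sent to the existing ISM as it occurs, whatever the site's attribution, and the ISM may call an ad hoc review on that basis.

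The two sections should also be reconciled on whether the between-cohort review follows the treatment period or the follow-up period.

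Any numeric seizure count for review should be left to the sponsor and the ISM, using a historical rate on the same more-than-one-AED definition. The 40% may not be that rate: Table 2 gives 38%, from the same trial, for receiving an anticonvulsant in the first postnatal week. The choice is sensitive to this. A count of 6 or more of 9 would be reached by chance 9.9% of the time at a true rate of 40%, but only 0.3% of the time at 20%.

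The cost is protocol wording, some ISM time, and an occasional chance review with a short enrolment pause. No dose or eligibility rule changes.
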